In order to assess the efficacy of the dose chosen for the double-blind study, we will also conduct a small open-label trial of the CBD solution prior to initiating the double-blind study. This open-label trial will enroll up to 12 participants who are interested in using CBD, and who have anxiety. This trial will determine whether patients derive clinical benefits at the current dosage proposed for the active treatment arm of the double-blind trial. This trial will examine all components of the originally proposed study.

Subjects will be recruited through IRB-approved advertisements and flyers in regions that have approved medical marijuana. Additionally, medical marijuana healthcare facilities throughout New England, including CannaCare, Integr8, MMJ Physician Practice, and others, may also refer interested patients to contact the study recruitment line for further screening. These healthcare groups provide their interested patients who meet for general inclusion criteria with study recruitment materials. The total sample size for the double-blind study is 40 (20 CBD, and 20 placebo); up to 15 of each group (30 total) will also complete the MRI scanning protocol. For the open-label trial, the total sample size is 12.

Inclusion Criteria:

- 1) Subject has provided informed consent
- 2) Subject is 18 or older
- 3) Subject is a native English speaker or acquired English prior to age 5
- 4) Subject scores a minimum of 16 on the Beck Anxiety Inventory (BAI) OR a minimum of 8 on the Overall Anxiety Severity and Impairment Scale (OASIS) at the screening visit

Exclusion Criteria:

Subjects will be excluded if they report any of the following:

- 1) Non-native English speakers
- 2) Estimated IQ < 75
- 3) Meets criteria for DSM-IV classification of current substance abuse/dependence, psychotic disorder, bipolar disorder, or an eating disorder
- 4) A first-degree relative with a psychotic disorder
- 5) A history of head injury or loss of consciousness greater than 5 minutes
- 6) Currently uses marijuana or cannabinoid-based products more frequently than 1x/month
- 7) Female subjects will be excluded if they have a positive urine pregnancy test, or if they are currently breastfeeding
- 8) Presence of a serious medical illness, including liver, kidney, or cardiovascular disease, or neurological disorder
- 9) Allergy to coconut oil

- 10) Current use of valproate
- 11) Currently enrolled in other research studies or clinical trials involving interventions

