### **Open-Label Trial**

Subjects will complete study visits at McLean Hospital. Following a preliminary phone screen and prior to any evaluation, all study subjects will be required to sign a McLean Hospital approved informed consent form that describes all study procedures. A structured clinical interview will be administered, and demographic information, substance abuse/use, and medical histories will also be obtained and reviewed with the study physician. Study inclusion/exclusion criteria will be applied, and appropriate subjects will be enrolled and complete the rest of the study visit.

For the first stage of the study, 12 individuals will be assessed at baseline and weekly for 6 weeks of treatment with sublingual CW solution in an open-label fashion: all subjects will receive the CBD product. Subjects will self-administer 0.5 ml (15mg) of CBD sublingually two times daily, in the morning and the evening, for a daily total dose of 30 mg CBD; if no clinical benefit (>15% reduction in BAI ratings) is evident at the 2-week visit, patients will be given the option to add an additional dose in the middle of the day to bring the total daily dose to 45mg CBD. At the weekly visits throughout the treatment period, individuals will complete clinical scales and have a check-in with study staff. In addition to clinical ratings and a check-in with study staff, neuropsychological testing will also be performed at baseline and week 6 in order to assess cognitive performance. A subset of individuals will receive an hour-long MRI scan at baseline and week 6, with both resting state and task-related functional magnetic resonance imaging (fMRI) in each MRI session. In addition, a brief diffusion tensor imaging (DTI) sequence will also be acquired to examine white matter fiber tract integrity, and magnetic resonance spectroscopy (MRS) will be conducted to examine levels of certain metabolites in the brain. Subjects will also provide a buccal swab sample for genetic analysis at the baseline visit; this will allow specification of genes related to degradative enzymes involved in the endocannabinoid system (e.g. FAAH, MAGL) and allow us to determine whether genetic profile can predict treatment response.

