### **Double-Blind Trial**

Individuals will be assessed in-person at baseline and weekly for 6 weeks of treatment with compounds administered as sublingual solutions in a double-blind, randomized procedure: subjects will receive either the CW solution or matched placebo. At the weekly visits throughout the treatment period, individuals will complete clinical scales and have a check-in with study staff.

In addition to clinical ratings and a check-in with study staff, neuropsychological testing will be performed at baseline and week 6 in order to assess cognitive performance. Finally, a subset of individuals will receive an hour-long MRI scan at baseline and week 6, with both resting state and task-related functional magnetic resonance imaging (fMRI) in each MRI session. In addition, a brief diffusion tensor imaging (DTI) sequence will also be acquired to examine white matter fiber tract integrity, and magnetic resonance spectroscopy (MRS) will be conducted to examine levels of certain metabolites in the brain. Subjects will also provide a buccal swab sample for genetic analysis at the baseline visit.

[figure not shown]
At the end of the baseline visit, eligible subjects will be randomized to either CW solution or placebo using a standard alternating procedure in accordance with the McLean Pharmacy. Subjects will be instructed on how to administer the compound, as described above.

For both the open-label and double-blind trials, the baseline and the final study visits are estimated to take approximately 3-4 hours, with the weekly visits in the interim estimated to take approximately 1 hour, and 15 minutes for phone check-ins, for a total of approximately 10-12 hours required to complete all possible visits. Urine samples will be collected at every other visit (Visits 1, 3, 5, and 7) to measure THC via GCMS (Quest Diagnostics) and to monitor for the presence of other substances throughout the study. Female subjects will be informed that their sample will also be used to confirm negative pregnancy (HCG) status; if at any point their urine tests positive for HCG, they will be excluded from the study. We are currently in communication with several groups that may be able to assess for CBD in urine; we hope to utilize one of these groups to quantify CBD in urine throughout the study.

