#### Neuropsychological Assessment

In addition to the clinical rating scales, the proposed investigation also includes a brief battery of neuropsychological tests to examine the potential effects of CBD on cognition in subjects with anxiety. Individuals will complete neuropsychological assessments at two time points; at baseline and after 6 weeks of treatment. The neurocognitive battery is primarily designed to evaluate frontal, executive, and memory functions as well as general intellectual capacity. The neuropsychological measures will be administered by a trained psychometrician and were chosen because they are standard, well-known measures that can be administered and scored reliably. Measures to be administered at baseline and both follow-up visits include the [REDACTED]

[REDACTED]. The neurocognitive assessment battery will take approximately 1.5 hours to complete. Many of these tests, including the [REDACTED] [REDACTED] have alternate versions to use at the follow-up visit, in order to reduce the likelihood that subjects remember portions of the assessments from baseline.

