## DATA AND SAFETY MONITORING

Describe the plan for monitoring the data to ensure the safety of subjects. The plan should include a brief description of (1) the safety and/or efficacy data that will be reviewed; (2) the planned frequency of review; and (3) who will be responsible for this review and for determining whether the research should be altered or stopped. Include a brief description of any stopping rules for the study, when appropriate. Depending upon the risk, size and complexity of the study, the investigator, an expert group, an independent Data and Safety Monitoring Board (DSMB) or others might be assigned primary responsibility for this monitoring activity.

NOTE: Regardless of data and safety monitoring plans by the sponsor or others, the principal investigator is ultimately responsible for protecting the rights, safety, and welfare of subjects under his/her care.

Data analyses will be conducted on the open-label phase of the study prior to initiating the double-blind phase in order to ensure that patients derive clinical benefit from the dose selected. Specifically, in conjunction with [REDACTED], we will assess clinical response after the first 5 patients have completed their 6 week trial. If we do not see clinical improvement based on a review of clinical scales, subjective reports and performance, we will consider increasing the dose to 1 droppers two times a day for a total of 60 mg CBD per day. Clinical improvement will be defined as a 15% reduction in BAI scores from baseline. Findings will be used to inform the double blind phase of the study, which would not begin until adequate dose/response is achieved. An amendment would be submitted to the IRB for approval prior to adjusting the dose of CBD.

In the unlikely event that an adverse event occurs, it will be reported to the primary investigator and the Institutional Review Board's guidelines will be followed to ensure adequate reporting and response. All adverse events will be reported to the Partners Healthcare Internal Review Board for their records. There are currently no plans to utilize a Data Safety Monitoring Board (DSMB) due to the extremely low side-effect profile of CBD, but if the IRB deems that an independent DSMB is necessary, the investigators would be happy to suggest individuals who are appropriate or to consider outside suggestions from IRB members.

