#### **STATISTICAL APPROACHES**

All statistical analyses will be conducted using IBM SPSS Statistics (version 28). Data will be screened for outliers and any data points more than 2 standard deviations from the group means will be excluded. Additionally, data will be screened for skew, kurtosis, non-normality, and homogeneity of variance. If the assumptions of parametric inferential analyses are not met, the appropriate non-parametric analyses (e.g. Wilcoxon-Signed Rank Test) will be performed. Descriptive statistics will be used to characterize the demographic data. Baseline clinical and neuropsychological data will be assessed using 2-tailed paired *t*-tests to compare follow-up timepoints to baseline values. When needed, Bonferroni corrections for multiple comparisons will be utilized.

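### The randomised double-blind phase has no CBD-versus-placebo analysis: every test the plan names compares follow-up with baseline within subjects

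*Combined protocol and SAP*

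**What the plan says.** The design sections describe two phases.

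- **Open-label phase** (Open-Label Trial): 12 participants, and "all subjects will receive the CBD product".
- **Double-blind phase** (Double-Blind Trial): "eligible subjects will be randomized to either CW solution or placebo". Research Design and Methods gives the size: "The total sample size for the double-blind study is 40 (20 CBD, and 20 placebo".

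The analysis is set out only in Statistical Approaches, a single paragraph that does not distinguish the phases. It says that baseline clinical and neuropsychological data "will be assessed using 2-tailed paired *t*-tests to compare follow-up timepoints to baseline values". If parametric assumptions fail, "the appropriate non-parametric analyses (e.g. Wilcoxon-Signed Rank Test) will be performed". Bonferroni correction is to be used when needed, with no alpha and no family of tests stated. Groups enter only through data screening: an outlier rule based on group means, and a check of homogeneity of variance.

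Specific Aims 1 and 2 are also worded as assessments before and after hemp treatment. They do not mention placebo.

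**The concern.** A paired test asks whether scores moved from baseline. That is a reasonable descriptive question for a single-arm phase. A placebo arm exists to answer a different one: whether scores moved more on CBD than on placebo. No section names a two-sample test, ANCOVA, mixed model, arm-by-visit term or any other contrast between arms.

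Statistical Approaches also does not say whether the paired tests are run in each arm or on both arms together. Either way, three sources of change are mixed with any CBD effect:

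- placebo response;
- regression to the mean in anxiety scores, because entry requires a high score at screening ("Subject scores a minimum of 16 on the Beck Anxiety Inventory (BAI) OR a minimum of 8" on the OASIS);
- residual practice effects on cognition. Neuropsychological Assessment says that many of the tests "have alternate versions to use at the follow-up visit", which does not claim that all do.

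The likely informal substitute is to set a significant CBD arm beside a non-significant placebo arm. That is not a test of the difference between them.

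**Working it through.** **Inputs from the documents.** 20 per arm; two-sided paired tests. The sample size comes with no alpha, effect size, SD, power or dropout rate, so there is no figure of the plan's own to reproduce.

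**Assumptions.** Two-sided alpha 0.05, one comparison, no dropout, no CBD effect, and the same improvement d (in SDs of the change score) in both arms.

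**Step 1: one arm, n = 20.** The paired t statistic is noncentral t with 19 df and noncentrality d√20, with critical value 2.093. For d = 0.3, 0.5 and 0.8 the noncentrality is 1.342, 2.236 and 3.578. The rejection probability p is 0.247, 0.565 and 0.924.

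**Step 2: arms read side by side.** The arms are independent, so P(CBD significant, placebo not) = p(1 − p):

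- d = 0: 0.05 × 0.95 = 0.0475
- d = 0.3: 0.247 × 0.753 = 0.186
- d = 0.5: 0.565 × 0.435 = 0.246
- d = 0.8: 0.924 × 0.076 = 0.070

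Since p(1 − p) cannot exceed 0.25, this reading peaks at about 25% and falls once both arms are usually significant.

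**Step 3: both arms pooled, n = 40.** With 39 df and noncentrality d√40, rejection is 0.457, 0.869 and 0.9985.

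**Step 4: between-arm test.** The shared change cancels, so the error rate is 5% at every d. A simulation of 40,000 trials per d (baseline to week-6 correlation 0.5) gave ANCOVA rejection of 0.048, 0.049 and 0.049.

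| Reading, no CBD effect | d = 0.3 | d = 0.5 | d = 0.8 |
|---|---|---|---|
| CBD arm alone | 25% | 56% | 92% |
| CBD significant, placebo not | 19% | 25% | 7% |
| Both arms pooled | 46% | 87% | 99.8% |
| Between-arm, baseline-adjusted | 4.8% | 4.9% | 4.9% |

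**Step 5: regression to the mean alone.** Suppose everyone qualifies on the analysed scale, the qualifying score is also the baseline, the cutoff is c SDs above the population mean, and the retest correlation is r. The expected fall is (1 − r)φ(c)/(1 − Φ(c)) SDs. With c = 0 and r = 0.8 this is 0.16 SD; with c = 1 and r = 0.6 it is 0.61 SD. In simulation (20,000 trials, n = 20) the paired test was significant in 20% and 88% of trials at these two ends, with no treatment effect and no placebo response.

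**Step 6: power of the missing test, 20 per arm.** For the unadjusted two-sample t-test (38 df, noncentrality δ√10), power is 34% at δ = 0.5 SD and 69% at 0.8 SD. With ANCOVA at an assumed correlation of 0.5 (37 df), the effect is divided by √(1 − 0.25) = 0.866, and power is 43% and 81%.

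**The case against.** The strongest reply is that this is an omission, not a wrong choice. The paired test is never expressly assigned to the double-blind phase. It suits the open-label phase, which is analysed first. Homogeneity of variance has no role in a paired t-test, so a group comparison may have been in mind, and the Wilcoxon test is only an example. This is fair as to intent. But the paragraph is the whole analysis plan for both phases, and screening language names no test, outcome, timepoint or estimate from which an arm comparison could be derived.

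Second, the illustration ignores the Bonferroni clause. If it were applied over six weekly visits (an assumed family, alpha 0.05/6 = 0.0083), the figures for d = 0.3, 0.5 and 0.8 become:

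- CBD arm alone: 8%, 27% and 73%;
- CBD significant, placebo not: 7%, 20% and 20%;
- pooled: 20%, 65% and 98.6%.

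The sizes depend on the correction, and so does the d at which the side-by-side rate peaks. The defect remains. The 2-SD outlier exclusion is not modelled either, so none of these are the plan's actual error rates.

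Third, no section says that the arms will be pooled or the CBD arm read alone. That is correct: those rows show what the text permits, and the largest figures belong only to them.

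Fourth, entry is by BAI or OASIS, so a person admitted on OASIS need not have a high BAI. The mechanism also does not carry over directly to cognition or imaging. Both points stand, and they make Step 5 an illustrative range. Placebo response alone is enough for the main argument.

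**Conclusion.** The concern holds and should be fixed before the double-blind data are analysed. No CBD-versus-placebo contrast is specified anywhere, and the tests that are named cannot supply one. This conclusion comes from reading the text and needs no numerical assumption.

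The size is illustrative, because the documents give neither alpha nor an expected change. At an uncorrected two-sided 0.05 with shared improvement of 0.3 to 0.8 SD, an ineffective product would look effective in 25% to 92% of trials if the CBD arm is read alone, and in 7% to 25% if the arms are set side by side. A between-arm test would give about 5%. Leaving the contrast unstated also means that it could be chosen after unblinding.

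**What to change.** In Statistical Approaches, treat the two phases separately.

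- **Double-blind phase.** State that efficacy is tested by comparing arms on the week-6 score, adjusted for the baseline score, using ANCOVA or an equivalent mixed model where weekly scores exist. Report the adjusted difference with its 95% CI, and state alpha.
- **Lead outcome.** BAI is the natural candidate if the sponsor confirms it as primary. It is already the response measure in the open-label phase, where Data and Safety Monitoring says "Clinical improvement will be defined as a 15% reduction in BAI scores from baseline".
- **Analysis set.** Name the set, starting from all randomised participants. Say how it relates to the 2-SD exclusion and to early termination. Week-6 ANCOVA on those with data is a complete-case analysis, and losses may differ by arm.
- **Other outcomes.** Use the same between-arm model for the other scales, the neuropsychological scores and the imaging measures. Imaging has at most 15 per arm, so the power figures above do not apply to it.
- **Paired tests.** Keep them for the open-label phase and as within-arm description.
- **Aims.** For the double-blind phase only, word them as change relative to placebo.

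The cost is a paragraph of text and a standard SPSS procedure on data the protocol already plans to collect. Visits, randomisation and sample size do not change. The price is candour about precision: without baseline adjustment, 20 per arm gives 80% power only for a difference of about 0.91 SD (t-test, two-sided 0.05).

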#### Clinical Ratings

The Structured Clinical Interview for DSM-V Patient Version (SCID-P) and the SCID-P Substance Abuse/Dependence Module or the Quick Structured Clinical Interview for DSM-V Disorders (QuickSCID) will be administered to all study participants during visit 1 by the Principal Investigator, a Clinical Neuropsychologist or trained Clinical Research Assistant. Subjects will also complete clinical rating scales and questionnaires that have been shown to provide reliable estimates of current clinical state and are easily administered. They will also complete quality of life measures. All subjects will be given the following measures at the baseline and final visits that take approximately one hour to complete:

Subjects will also complete a subset of these measures, specifically the anxiety and mood-related measures [REDACTED], along with the SEQ, at each weekly visit. An Abuse Liability Rating Scale (ALR) will be completed at V3 and V7.

Please note that if suicidality is endorsed spontaneously, on any of the clinical scales, or during the SCID or weekly check-ins with study staff, the patient will be immediately assessed for suicidality risk. Please see “Suicidality SOP” attachment for further information.

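### Weekly anxiety scores are never analysed jointly: the plan names only two-timepoint tests against baseline and fixes no main between-arm contrast

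*Combined protocol and SAP*

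**What the plan says.** The Double-Blind Trial section sets the schedule: "Individuals will be assessed in-person at baseline and weekly for 6 weeks of treatment". It adds: "At the weekly visits throughout the treatment period, individuals will complete clinical scales and have a check-in with study staff". Clinical Ratings confirms that anxiety is in the weekly set: "Subjects will also complete a subset of these measures, specifically the anxiety and mood-related measures" are completed "at each weekly visit". The names of the scales are redacted, which is not a fault of the plan.

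Statistical Approaches is one short paragraph. "Baseline clinical and neuropsychological data will be assessed using 2-tailed paired" t-tests are to be used "to compare follow-up timepoints to baseline values". If assumptions fail, "the appropriate non-parametric analyses (e.g. Wilcoxon-Signed Rank Test) will be performed". Bonferroni correction is mentioned for use where required, without a number of comparisons. The paragraph names no mixed model, repeated-measures ANOVA, slope, area under the curve or average over weeks. It also names no primary timepoint, no between-arm comparison and no handling of missing visits.

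Research Design and Methods gives the double-blind sample size as 40, with 20 per arm. No power calculation, standard deviation, correlation or dropout rate accompanies it.

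**The concern.** Each participant supplies up to six follow-up anxiety scores. A paired t-test or signed-rank test uses one of them together with baseline, and the other five contribute nothing to that estimate. With 20 per arm and no stated power, two things are at stake.

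- **Precision.** A single weekly score carries that week's full fluctuation. If the quantity of interest is the effect late in treatment, averaging several weeks reduces that noise at no extra cost.
- **Retention.** Someone who attends five of six weekly visits is lost from the test of the missed week, although the other scores say something about the missing one.

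A between-arm test at a single week would address neither, so the point is distinct from the absence of an arm comparison in the same paragraph. One rewrite can deal with both.

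**Working it through.** **Plan's own figure.** There is none to reproduce: the 20 per arm comes with no effect size, SD, alpha or power.

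**Inputs from the documents.** 20 per arm; baseline plus six weekly scores; two-sided testing.

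**Assumed inputs.** Alpha 0.05; power 80%; correlation of baseline with each follow-up r0 = 0.4-0.6; correlation between follow-ups r1 = 0.6-0.8; equal SD at each visit. Results are in SD units of one weekly score.

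**1. Mean of weeks 4-6 against one week, both adjusted for baseline, constant effect.** With k = 3 weeks averaged:

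Variance ratio = [(1 + (k − 1)r1)/k − r0²] / (1 − r0²)

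- r0 = 0.5, r1 = 0.7: (0.800 − 0.250)/0.750 = 0.733. Equivalent sample size 1/0.733 = 1.36, or 36% more patients.
- r0 = 0.6, r1 = 0.6 (most favourable): (0.733 − 0.360)/0.640 = 0.583, or 71% more.
- r0 = 0.4, r1 = 0.8 (least favourable): (0.867 − 0.160)/0.840 = 0.841, or 19% more.
- Outside the range, r0 = 0.5, r1 = 0.9: (0.933 − 0.250)/0.750 = 0.911, or about 10% more.

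Detectable between-arm difference, normal approximation, central case:

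- one week: 2.80 × √(2/20 × 0.750) = 0.77 SD (0.79 SD by noncentral t)
- weeks 4-6 mean: 2.80 × √(2/20 × 0.550) = 0.66 SD

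**2. The same contrast if benefit grows linearly from zero at baseline to week 6.** The weeks 4-6 mean then carries (4 + 5 + 6)/(3 × 6) = 0.833 of the week-6 effect. Signal-to-noise relative to week 6 alone is 0.833 divided by the square root of the variance ratio:

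- central: 0.833/√0.733 = 0.833/0.856 = 0.97
- least favourable: 0.833/√0.841 = 0.91
- most favourable: 0.833/√0.583 = 1.09

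In the central case, averaging helps only if the mean effect over weeks 4-6 exceeds about 86% of the week-6 effect.

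**3. Week 6 as the target.** A joint model of all weekly scores was compared with a baseline-adjusted analysis of week-6 completers, using known-covariance generalised least squares. Dropout was spread evenly over the six weeks. The assumed correlation structures were equal correlation 0.5, equal correlation 0.7, and first-order autoregressive 0.8.

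- Complete data: identical variance (for example 0.0750 against 0.0750 at correlation 0.5), so no gain.
- 20% dropout, equal correlation 0.5: 0.0906 against 0.0938. √(0.0906/0.0938) = 0.983, so the SE is 1.7% smaller.
- 10-30% dropout over the three structures: SE 0.8% to 4.1% smaller.

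**Scope.** The neuropsychological battery is given only at baseline and week 6, so there are no intermediate scores to use.

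**The case against.** The strongest reply is that the large gain comes from changing the question. The Specific Aims speak of ratings before and after treatment, and the final scales follow six weeks of treatment, so the end-of-treatment effect is a natural target. For that target the intermediate scores add almost nothing when data are complete. A baseline-adjusted comparison at week 6 would be a legitimate main analysis, and nothing in the documents singles out weeks 4-6. This stands, and it limits the point.

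A reader might infer that the plan simply forgoes precision worth 19-71% more patients. The documents do not support that. The figure needs a roughly constant effect over weeks 4-6 and correlations that the documents do not give; under linear onset it roughly cancels or reverses. The open-label phase looks for BAI benefit at the 2-week visit, and the investigators' earlier trial lasted 4 weeks. That hints at earlier onset, but neither fact is a time course. The single-week comparator is also hypothetical, since the plan names no between-arm estimate.

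A reader might also infer that the plan commits to six separate weekly tests. It does not say which follow-ups will be tested; it says only that the tests are paired.

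What the reply does not remove is that no primary timepoint is fixed for averaging to displace, no joint analysis is named, and missed visits are unaddressed.

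**Conclusion.** The point holds in a limited form. The weekly anxiety and mood scores enter the plan only through two-timepoint tests against baseline, and a missed week removes the participant from that week's test. One prespecified between-arm contrast from a joint model is better whichever target is chosen, but the benefit differs:

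- **Weeks 4-6 mean, effect roughly constant:** variance 0.58-0.84 of the single-week value, 0.73 in the central case.
- **Weeks 4-6 mean, linear growth to week 6:** about even, 0.97 (0.91-1.09).
- **Week 6:** mainly retention of participants with missed visits, about 0-4% in SE.

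All of these rest on assumed correlations, and the last also on assumed dropout. The point is worth acting on because the remedy is cheap, not because a fixed gain in precision is assured.

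**What to change.** For the weekly clinical scales in the double-blind phase, replace the separate paired tests with one mixed model of all weekly scores, with terms for arm, week, arm-by-week and baseline score. Prespecify one between-arm contrast as the main estimate, either the mean of weeks 4-6 or week 6, and give the reason for the choice. Show the other weeks descriptively. State the missing-data assumption: the model uses the available weeks of a participant with a gap on the basis that data are missing at random. If a simple per-person mean is used instead, a rule for incomplete weeks is needed. Leave the neuropsychological tests out of this model.

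The cost is SAP wording; the model is available in SPSS and needs no new data. The drawback of the averaged contrast is that it answers a late-treatment average rather than the end-of-treatment effect, and it is diluted if benefit is still growing at week 6.

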## **BACKGROUND AND SIGNIFICANCE**

Provide a brief paragraph summarizing prior experience important for understanding the proposed study and procedures.

*Cannabis sativa* has been used medicinally for a range of disorders for thousands of years, including anxiety. Cannabis is comprised of more than 100 cannabinoids; D-tetrahydrocannabinol (Δ9-THC) is the major psychoactive constituent, and cannabidiol (CBD) is the major non-psychoactive constituent that has been touted to have a variety of potential medicinal benefits. Industrial hemp is a variety of the *Cannabis sativa* plant, which until recently was grown specifically for industrial uses, such as textiles. Hemp has much lower concentrations of THC than cannabis, defined as THC<0.3% by weight. In recent years, some hemp strains have been bred to produce particularly high concentrations of CBD with very low concentrations of THC, virtually eliminating the potential for intoxicating effects. Extracts from these hemp strains are manufactured into a variety of oils, capsules, sprays, etc., available in brick-and-mortar stores across the country as well as on the Internet.

Previous studies have demonstrated CBD's acute anxiolytic potential in both animals and humans. Recently, our group began the first ever clinical trial of a high-CBD compound for anxiety. This trial, studied under IND [REDACTED], examines the impact of a high-CBD, low-THC cannabis-derived sublingual solution on measures of anxiety, mood, quality of life, and cognition over a 4-week treatment period. Interim analyses completed on the first 5 subjects who completed the trial were extremely compelling; analyses indicate that patients reported a 68.29% reduction in anxiety symptoms on the primary outcome measure, the Beck Anxiety Inventory (BAI), from the baseline to final visit. The study product is very well-tolerated, with no serious adverse events occurring to date.

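### Cheap improvement, not an error: Holm's step-down procedure could replace Bonferroni at the same familywise error, never rejecting less and sometimes more

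*Combined protocol and SAP*

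**What the plan says.** The Statistical Approaches section gives a single sentence on multiplicity: "When needed, Bonferroni corrections for multiple comparisons will be utilized". It names no other procedure. It does not say which tests form a family, how many there are, or at what alpha.

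The planned inferential test in the same section is a within-subject one: "Baseline clinical and neuropsychological data will be assessed using 2-tailed paired" t-tests are used "to compare follow-up timepoints to baseline values", with a non-parametric substitute if assumptions fail. No between-arm test is named.

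Several comparisons are likely. The Double-Blind Trial section states: "Individuals will be assessed in-person at baseline and weekly for 6 weeks of treatment". That allows up to six comparisons with baseline on each weekly scale. The Neuropsychological Assessment section adds a multi-test battery at baseline and week 6: "The neurocognitive battery is primarily designed to evaluate frontal, executive, and memory functions as well as general intellectual capacity". Research Design and Methods gives 20 subjects per arm in the double-blind phase and up to 12 in the open-label phase.

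**The concern.** Once a correction is applied, the choice of method affects how many real changes are declared significant. Bonferroni holds every p-value in the family to alpha/m. Holm holds only the smallest to alpha/m and relaxes the threshold after each rejection, with the same familywise guarantee.

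The groups are small and the outcomes many. A uniformly less powerful correction can leave some real changes in Aims 1 and 2 reported as non-significant, with no gain in error control. This is a point about efficiency. The validity of the planned correction is not in doubt.

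**Working it through.** **No plan figure to reproduce.** The documents state no power, alpha, adjusted alpha or sample-size calculation.

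**Inputs from the documents:** two-sided paired t-test; six weekly follow-ups; n=20 per arm or n=12 open-label, taking every subject as completing.

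**Assumed inputs:** familywise alpha 0.05; family of m=6; standardized change of 1.0 SD (n=12) or 0.8 SD (n=20); equal correlation of 0.5 to 0.7 between tests; six, three or one of the six effects real.

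**Step 1. Bonferroni does its job.** With independent tests at 0.05 each, the family error is 1 − 0.95^6 = 0.265. At 0.05/6 = 0.00833 each, it is 1 − (1 − 0.00833)^6 = 0.049.

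**Step 2. Holm gives the same guarantee.** Order the p-values and compare them with 0.05/6, 0.05/5, 0.05/4, 0.05/3, 0.05/2 and 0.05/1, that is 0.0083, 0.0100, 0.0125, 0.0167, 0.0250 and 0.0500. Stop at the first failure.
- Suppose m0 nulls are true. When the first of them is wrongly rejected, at most m − m0 hypotheses have already gone, so the threshold is at most alpha/m0.
- A false rejection therefore needs the smallest of m0 true-null p-values to be at or below alpha/m0. That has probability at most alpha under any dependence.
- Every Holm threshold is at least alpha/m, so Holm keeps all of Bonferroni's rejections.
- The smallest p-value faces the same threshold under both, so the chance of at least one rejection is identical.

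**Step 3. Bonferroni power by formula.** Power is the probability that a noncentral t with n − 1 degrees of freedom and noncentrality d√n exceeds the two-sided critical value at 0.00833.
- n=12, d=1.0: noncentrality 3.464, critical value 3.208, power 0.609.
- n=20, d=0.8: noncentrality 3.578, critical value 2.944, power 0.729.

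**Step 4. Simulation of both methods on the same data** (10,000 to 20,000 trials per setting). The table shows mean power per true effect.

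| Paired design | Real effects | Bonferroni | Holm |
|---|---|---|---|
| n=12, 1.0 SD, correlation 0.5–0.7 | 6 of 6 | 61% | 74–75% |
| n=12, 1.0 SD, correlation 0.5–0.7 | 3 of 6 | 61% | 65% |
| n=12, 1.0 SD, correlation 0.5–0.7 | 1 of 6 | 61% | 61% |
| n=20, 0.8 SD, correlation 0.6 | 6 of 6 | 73% | 84% |
| n=20, 0.8 SD, correlation 0.6 | 3 of 6 | 73% | 76% |
| n=20, 0.8 SD, correlation 0.6 | 1 of 6 | 73% | 73% |

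In the first row, one run reached 76% at correlation 0.5.

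With all six effects real, the chance of detecting all six rises from 20–29% to 56–63% (n=12) and from about 40% to 72% (n=20). The chance of at least one rejection is the same for both methods (95.8% in the n=20 row with six real effects). With three of six real, the familywise error is about 2% for Bonferroni and 3–4% for Holm, both under 5%.

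**Step 5. Wider range.** For the paired test with n=20, take m of 2, 6 or 12, effects of 0.5 to 1.0 SD and correlation 0 or 0.6. The gain is 1.4 to 18.6 points if all effects are real, and 1.0 to 5.1 points if half are (m of 6 or 12). If only one is real it is 0.0 to 0.3 points, a range that also covers the two-sample version.

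**The case against.** Bonferroni is a legitimate choice. It has one fixed threshold, is easy to explain and gives simple matching simultaneous confidence intervals. Nothing in the documents is made invalid or biased by using it. This stands, and it is why the point is an optional improvement. The interval advantage carries little weight here because the plan specifies no simultaneous intervals.

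A reader might infer that the trial is giving up true effects for nothing, or that the lost power is known to be material. The documents do not support either reading. They state no family size, alpha, effect size or number of real effects, and the lists of scales and cognitive tests that would help fix the family size are redacted. The large gains need most or all effects in the family to be real. That is plausible for repeated weekly ratings on one scale if a change appears early and lasts. It is less assured across cognitive tests.

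A reader might also infer that Holm would recover treatment effects. It would not, because the named tests compare follow-up with baseline. A rejection may reflect placebo response, regression to the mean after selection on an anxiety threshold, or practice on cognitive tests. Gains computed for a two-sample comparison of 20 against 20 (0.5 to 14.5 points if all effects are real) concern a test the plan does not name.

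It can also be said that the sentence leaves the family and the trigger for correction undefined, so that swapping method names repairs little. That is a separate and larger gap, and Holm neither worsens nor closes it. It does not remove the case for the better method once a family is set.

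**Conclusion.** The point holds as a low-cost efficiency improvement. Holm's familywise control and its never rejecting less than Bonferroni are mathematical facts that need no assumptions about this trial. The size of the gain does need them. At an assumed alpha of 5% with six paired tests, it is about 11 to 14 points of mean power if all six effects are real (73% to 84%, 61% to 74–75%), about 3–4 points if half are, and about zero if one is. The chance of finding at least one significant result is unchanged throughout. Bonferroni as planned is valid, and any extra rejections would be evidence of change from baseline only.

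**What to change.** In Statistical Approaches, replace the reference to Bonferroni corrections with the Holm step-down procedure, applied within each family of tests to which the correction would have been applied, and state that Holm-adjusted p-values will be reported.

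The cost is one sentence. The p-values may need to be sorted by hand or in a spreadsheet; because the section says all analyses are done in SPSS, a clause allowing this step would keep the text consistent. Simultaneous confidence intervals become less direct, which matters only if the plan later adds them. Defining the families, the alpha and when the correction applies is a separate change that could be made in the same edit.
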